**1 PROTOCOL SYNOPSIS**

Title	Controlled Focal Fibrous Band Release Method
Short Title	CONFIRM
IDE No.	G200312
Study Device	Avéli (formerly Deployable Hook)
Intended Use	The intended use of the subject device is to separate tissue (fibrous septa) and provide transillumination for anatomical navigation.
Proposed Indications for Use	Avéli is indicated for temporary reduction in the appearance of cellulite in the buttocks and thigh areas of adult females as supported by clinical data demonstrating benefits through three months of observation.
Study Design	Single arm, multicenter, open label pivotal study
Study Objective	Demonstrate safety and effectiveness of the deployable hook in reducing the appearance of cellulite
Study Duration	1-year participant follow-up
Number of Sites	7 sites in United States and 2 sites in Australia
Enrollment	74 participants, including 6 roll-in patients
Primary Effectiveness Endpoint	Mean change (improvement) from baseline in the Cellulite Severity Scale (CSS)  is $\geq 1$ point at 3 months.
Primary Safety Measure	Absence of device related Serious Adverse Events (SAEs) directly attributable to the device at 30 days.

---

 CSS = CSS-A (Number of Evident Depressions) + CSS-B (Average Depth of Depressions) – 1

**Abbreviated CONFIRM Protocol**

Secondary Inferential Effectiveness Endpoints	

• The CSS score at 3 months. A participant is considered a responder if the 3 month CSS score has improved by at least 1 point from the baseline CSS score.

• The GAIS score at 3 months as determined by blinded and independent evaluators. A participant is considered improved if the GAIS assessment is improved (1), much improved (2) or very much improved (3).

• The patient satisfaction assessment measured at 3 months. Patient satisfaction is collected using an evenly balanced scale with 5 categories: very satisfied, satisfied, neither satisfied nor dissatisfied, dissatisfied, very dissatisfied. The general “Satisfied” category is defined as those that indicated they were satisfied or very satisfied with their outcome.

--	---

## 2 STUDY POPULATION

### 2.1 INCLUSION CRITERIA

Participants eligible for inclusion in this study must fulfill the following criteria:

1. Female age 21 to 55 years
2. Moderate to severe cellulite in the thighs and/or buttocks, with a minimum of 5 depressions of moderate (or more severe) depth
3. Cellulite Severity Score (CSS)  $\geq 3$
4. Will commit to not trying any other cellulite treatments through 12-month follow-up
5. Ability and willingness to provide written informed consent in English
6. Negative urine pregnancy test

### 2.2 EXCLUSION CRITERIA

Participants will be excluded from this study if they meet any of the following criteria:

1. In the last 12 months, underwent a cellulite procedure on the buttocks and/or thighs
2. Previous liposuction on the buttocks and/or thighs
3. Intends to lose greater than 10% of body weight during study follow-up
4. Greater than 10% increase or decrease in body weight within the last six (6) months or any history of weight loss greater than 60 kg/132 lb.
5. Physician assessed severe skin laxity, flaccidity, and/or sagging in targeted regions.
6. Has taken any of the following within 14 days of study procedure:
  - a. NSAIDs (aspirin, ibuprofen, naproxen); or,
  - b. Vitamin E, herbal teas or dietary supplements (e.g. Ginkgo Biloba, Willow Bark)
7. Intends to take the following medications within 14 days after procedure
  - a. NSAIDs (aspirin, ibuprofen, naproxen); or,
  - b. Vitamin E, herbal teas or dietary supplements (e.g. Ginkgo Biloba, Willow Bark)
8. Known clotting defects, bleeding disorders, or severe anemia ( $\geq$  Grade 3, NCI)
9. Active dermatologic condition including rash, eczema, psoriasis, or skin cancer in target regions
10. BMI  $\geq 30.0$
11. Evidence of an active infection or fever greater than 38°C/100.4°F on day of index procedure.
12. Current or recent smoker, or use of nicotine (within 6 months)
13. History of cardiopathy, hypertension, diabetes or hypoglycemia, or pneumopathy

---

 Participants can be treated unilaterally or bilaterally

  $\leq 7.9$  g/dL hemoglobin

**Abbreviated CONFIRM Protocol**

14. History of peripheral vascular disease, large varicose veins, pedal edema, reduced lower extremity pulses, personal history of connective tissue disease, or family history of Ehlers Danlos disease
15. Planning to get pregnant in next year, or currently pregnant or breastfeeding
16. Has atrophic scars, or a history of atrophic scars or keloids
17. Any participant who is currently participating or considering participation in any other research of an investigational drug or device which may overlap study follow-up
18. Any condition(s) that in the Investigator's opinion, might indicate the participant to be unsuitable for the study, such as co-existing psychiatric illness.
19. Unable to complete data entry into patient health questionnaires due to unwillingness, no computer or internet ready device, or, cannot gain access to internet, or, does not speak English.

**3 STUDY PROCEDURES****3.1 SCHEDULE OF EVENTS**

The summary of required visits and testing is provided in **Table 1**.

**Table 1 Schedule of Events**

Protocol Requirements	Screening / Baseline	Pre-Procedure	Procedure	24-hours	7 Days	1 Month 	3 Months 	6 Months	12 months
		Day 0	Day 0	18-48 hours Remote	± 3 days Remote or Clinic	+ 2 weeks Clinic	-2 weeks-+ 4 weeks Clinic	± 4 weeks Clinic	± 4 weeks Clinic
Informed Consent 	X								
Demographics	X								
Inclusion/Exclusion Criteria	X	X							
Medical and surgical history	X								
BMI	X					X	X	X	X
Participant Reported Questionnaires  :									
Procedure Goals	X						X	X	X
Recovery 				X	If indicated	If indicated	If indicated	If indicated	If indicated
Discomfort and Soreness, Pain VAS 			X 	X	X	X	X	If indicated	If indicated
QOL and Satisfaction							X	X	X
Participant Symptom Diary 				X	X	X			

 30 days is also referred to as 1-month visit

 For purposes of scheduling, the protocol definition of a month is 30 days. Week refers to 7 days.

 Prior to any study specific procedures; participant may need to be re-consented if protocol is amended.

 Participants should complete via their private ePRO login with the exception of Pain VAS at procedure and Discomfort, Soreness Pain VAS questionnaires if indicated after 3M visit.

 Administered until participant returns to normal activities.

 Daily completion of Discomfort, Soreness and Pain VAS through 7 days post-procedure.

 Only VAS Numeric Pain Distress Scale administered during and after the procedure (before discharge).

 Participants to complete weekly, four (4) times through 28 days post-procedure.

Abbreviated CONFIRM Protocol

Protocol Requirements	Screening / Baseline	Pre-Procedure	Procedure	24-hours	7 Days	1 Month 	3 Months 	6 Months	12 months
		Day 0	Day 0	18-48 hours Remote	± 3 days Remote or Clinic	+ 2 weeks Clinic	-2 weeks+ 4 weeks Clinic	± 4 weeks Clinic	± 4 weeks Clinic
Physical Exam 	X								
Standard Photography	If done				If Clinic 				
Study Photography		X 				X	X	X	X
Marking the insertion sites and depressions to be treated		X							
Pregnancy test 		X							
Vitals		X							
Deployable Hook Procedure			X						
Con. Medications/ Treatments	Captured and Updated From -30 days to Study Exit								
Adverse Event  Assessment	Monitored throughout study								
Study Exit									X 
Independent Evaluators									
CSS A and B							X	X	X
Blinded 'After' Assessment							X	X	X
GAIS							X	X	X

 Includes physical examination on target areas for severity assessments in laxity and depressions, and exclusionary abnormalities. In follow-up, this activity is covered under AE assessment.

 If visit done at clinic, photos per the clinic standard of care should be captured

 Must be done before and after markings and always before the procedure

 Required only for fertile, pre-menopausal women.

 Adverse Event collection starts when the Deployable Hook procedure is initiated. At each visit, ongoing AEs should be assessed along with participant interview/examination for potential new AEs

 At completion of 1 year, or earlier if participant withdrawn

#### 4 QUESTIONNAIRE CATEGORIES

The set of participant questionnaires developed for this study address a range of clinically important issues (**Table 2**) including behavioral/perception impact, procedure and recovery experience, along with cellulite treatment results satisfaction and expectations. The time to complete the questionnaires is <20 minutes.

**Table 2 Participant Questionnaire Concepts**

Concept	Time to complete	When to complete
1. Procedure objectives /goals	<5 minutes	Baseline, 3, 6, and 12 months
2. Recovery duration	1 minute	Every visit until return to pre-procedure activity is reported
3. Soreness/discomfort in recovery	1 minute	Daily for 7 days post-procedure; 30 day, 3 month, and thereafter will be administered by site if indicated*
4. VAS Numerical Pain Distress Scale	1 minute	During and after the procedure (before discharge) and daily for 7 days post-procedure; 30 day, 3 month, and thereafter will be administered by site if indicated*
5. Behavioral impact of cellulite	<5 minutes	3, 6 and 12 months
6. Outcome satisfaction and procedure experience	1 minute	3, 6, and 12 months
7. Participant symptom diary	3 minutes	Once a week for the first 4 weeks after index procedure.
* Administered by study personnel, will not be in ePRO		

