#### **6.5.4 Secondary Endpoint 3 (Inferential) – Patient Satisfaction at 3 months**

Endpoint Definition: The patient satisfaction assessment measured at 3 months. Patient satisfaction is collected using an evenly balance scale with 5 categories: very satisfied, satisfied, neither satisfied nor dissatisfied, dissatisfied, very dissatisfied. The general “Satisfied” category is defined as those that indicated they were satisfied or very satisfied with their outcome.

Hypothesis:

Ho:  $p \leq 60\%$

Ha:  $p > 60\%$ ,

where  $p$ =proportion satisfied and 60% is an assumed acceptable performance goal for this endpoint and trial size.

Analysis cohort: The mITT cohort.

Statistical Analyses: The count and proportion of participants satisfied with their outcome will be summarized along with an exact binomial 2-sided 95% confidence interval for the proportion of responders along with a p-value. Additionally, count and proportions will be summarized for each of the 5 levels of patient satisfaction.

Definition of Success: If the lower bound of the 2-sided 95% confidence interval is greater than or equal to 0.6 then we will reject the null hypothesis and declare proportion of responders are greater than 60%.

Power calculation: The sample size for this trial is based upon the primary endpoint. With an observed performance of 67% satisfied in initial pilot data and expected sample size of 54, a one-sided alpha of 0.025 and performance goal of 60%, there will be ~17% power to test this hypothesis, however it is believed performance will be better in this trial.

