## 6.7 EXPLORATORY ANALYSIS

Additional exploratory statistical analysis may be performed including subgroup analyses and participant reported outcomes.

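### The behavioral-impact and QOL items have no baseline administration, so this single-arm trial cannot estimate their change from baseline

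*Combined protocol and SAP*

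**What the plan says.** Section 4 says that the participant questionnaires "address a range of clinically important issues" and includes behavioral and perception impact among them. Table 2, row 5, is "Behavioral impact of cellulite", with a completion time under 5 minutes and administration at months 3, 6 and 12. Row 6, on outcome satisfaction and procedure experience, is given at "3, 6, and 12 months". Row 1, on procedure objectives and goals, is given at "Baseline, 3, 6, and 12 months".

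In Table 1 (Section 3.1), the row "QOL and Satisfaction" is marked under 3, 6 and 12 months. Its Screening/Baseline and Pre-Procedure cells are empty.

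The synopsis describes the trial as a "Single arm, multicenter, open label pivotal study". On analysis, Section 6.7 says: "Additional exploratory statistical analysis may be performed including subgroup analyses and participant reported outcomes". The only inferential participant-reported endpoint is in Section 6.5.4, defined as "The patient satisfaction assessment measured at 3 months".

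**The concern.** A score for how much a condition affects behavior or quality of life needs a reference value. In a randomised trial the control arm can supply one; in a single-arm trial it has to be the participant's own pre-treatment value. Here there is neither. A 3-month answer could not be read as better, worse or unchanged relative to the state before the procedure.

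A current-state answer from before the procedure cannot be collected once the participant has been treated. The plan collects these items three times per participant, and exclusion criterion 19 keeps out women who cannot complete the questionnaires, so the data are evidently meant to be used. What is at stake is whether they can describe change since before treatment, or only the level of impact after it.

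**Working it through.** There is no figure in the plan to reproduce. The check is a reading of the two schedules side by side, followed by a count.

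**Schedule**

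| Item | Source | Baseline | Month 3 | Month 6 | Month 12 |
|---|---|---|---|---|---|
| Procedure goals | Table 1; Table 2 row 1 | yes | yes | yes | yes |
| Behavioral impact | Table 2 row 5 | no | yes | yes | yes |
| QOL and satisfaction | Table 1 | no | yes | yes | yes |
| Outcome satisfaction, procedure experience | Table 2 row 6 | no | yes | yes | yes |

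**Is this a table-extraction fault?** Unlikely. The Procedure Goals and BMI rows of Table 1 do carry a Screening/Baseline mark, so the column can be read. Table 2 states its timing in words and agrees with Table 1.

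**Are the two labels the same form?** Table 2 has no row called QOL. The matching visits suggest that the QOL part of the Table 1 row is the behavioral-impact form, but the documents do not say so. The conclusion does not depend on it, because neither label has a baseline.

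**Comparisons available per participant**
- As planned: three administrations give 3 × 2 / 2 = 3 within-participant differences (months 3 to 6, 3 to 12 and 6 to 12). Differences from baseline: 0.
- With one baseline administration: 4 × 3 / 2 = 6 differences, of which 3 are from baseline.

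**Participants concerned.** Section 6.3.7 gives 54 increased by 25%: 54 × 1.25 = 67.5, rounded up to 68. The synopsis gives 74 enrolled including 6 roll-ins, and 74 − 6 = 68, which agrees. Section 6.1.1 excludes roll-ins from the mITT cohort. Those with a planned pre-treatment value number 0 of 68 in the mITT cohort, and 0 of 74 with roll-ins.

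**Endpoints that use the item.** Primary: change in CSS. Inferential secondary: CSS responders, GAIS and satisfaction. None uses behavioral impact or QOL, and satisfaction with the outcome is a post-treatment rating that needs no baseline.

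**Added burden.** Behavioral impact takes under 5 minutes, and Procedure Goals, already given at baseline, takes under 5 minutes. Together that is under 10 minutes, below the 20-minute ceiling in Section 4.

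**The case against.** The strongest objection is that the form is not shown. The questionnaires were developed for this study, and the documents give no items, recall period or scoring. If the items ask participants to compare themselves with the time before treatment, post-treatment timing is coherent. This stands as a condition on the point. It does not remove it: such answers would be retrospective ratings by participants who know that they were treated, not measured change. Table 2 also names the concept as the impact of cellulite and lists it apart from outcome satisfaction, which fits a state that exists before treatment. Procedure Goals is given at baseline, but nothing says that it measures behavioral impact.

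The second objection is that nothing promised fails. The study objective and proposed indication concern the appearance of cellulite, no section commits to a change from baseline in these items, and Section 6.7 only permits participant-reported analyses. This stands in full and sets the size of the point.

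A reader might infer more than the documents support in three ways:
- **That no change at all can be measured.** Change between months 3, 6 and 12 can be.
- **That the plan contradicts itself or weakens an endpoint.** The two tables agree, and no endpoint uses the item.
- **That a baseline would let the trial show a treatment effect on quality of life.** In an uncontrolled, open-label study, a pre-post change in self-report remains open to expectation effects and regression to the mean.

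**Conclusion.** The point holds as a low-cost improvement and not as a threat to the trial's conclusions. As scheduled, no planned participant has a pre-treatment value for the behavioral-impact or QOL items, so change from baseline cannot be estimated for anyone. The data can describe the level of impact after treatment and its course from month 3 to month 12.

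The conclusion rests on one assumption that the documents do not settle: that the items ask about current impact. The effect is confined to the optional exploratory analyses in Section 6.7 and to any later statement that behavior or quality of life improved.

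**What to change.** In Table 1, mark the behavioral-impact/QOL part at Screening/Baseline, splitting the row if needed so that outcome satisfaction stays at months 3, 6 and 12. In Table 2, row 5, add Baseline to the timing. In Section 6.7, say that change from baseline will be summarised descriptively, and that an uncontrolled, open-label pre-post change does not by itself establish a treatment effect. State also whether the QOL part of the Table 1 row and row 5 of Table 2 are the same form.

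The cost is under 5 minutes of ePRO time per participant, at a visit that already collects Procedure Goals, plus a protocol amendment. Section 8.7 requires prior written IRB/HREC approval for that, and FDA approval if required, across 7 US and 2 Australian sites.

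For participants already treated, the amendment cannot help. Report their results as post-treatment description only, with no claim of improvement. If no amendment is made, the same statement should cover the whole trial.

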##### 4.1 MEDICAL PHOTOGRAPHY

Digital photography will be utilized in the assessment of the primary endpoint and other efficacy measurements at the intervals outlined in **Table 1**. The evaluations will occur in advance of each planned interim analysis as outlined in **Table 3**, and will follow the order outlined to ensure no pre-mature unblinding of the before/after that is required for the GAIS evaluation.

The medical photography which the independent evaluators will use, with a prescribed methodology, is distinguished here with name “Study Photography”, is described below.

Photographs captured outside of the study photography protocol, using methods normally used if not in a trial, will be included in the study dataset, but not utilized for endpoints, and will be referred to as “Standard photography”.

#### 4.1.1 Study Photography

The study endpoint relies on quality and consistent imaging. As such, it is imperative the images are taken under strict, standardized environments with only qualified photographers that are trained to the same methods. The Sponsor will ensure photographers are available for each site throughout the study and, if necessary, provide a contracted medical photographer. A chief photographer will be identified to develop and conduct training for all study site photographers. The training manual will outline the specific set-up including equipment, lighting, participant angles, and camera positioning.

Participants will be given reminders to wear loose fitting clothes without seams on the buttock or posterior thigh portions of the clothes before each required study photography visit and to prepare to stand until compression lines disappear, if present.

Prior to uploading images into the study database, the image metadata will be modified to include the participant ID and any date, location. PHI will be redacted.

For each photo session, the participant will stand and wear the provided standardized photographic garment as described in the CONFIRM imaging protocol. The participant will be instructed to relax muscles and stand at ease.

All study photography from this study are the property of the Sponsor and may be utilized for clinical development, scientific communication, marketing, regulatory purposes, and/or legal applications as required/desired by the Sponsor.

## 4.2 INDEPENDENT IMAGE EVALUATION

### 4.2.1 Selection and Qualification of Evaluators

The primary endpoint and other effectiveness outcomes involving study photography will be independently evaluated by three (3) physicians with medical aesthetics specialty, cellulite or body contouring experience. The evaluators will not participate in the study, will not be on staff of any CONFIRM study sites, and will have no financial interest in study sponsor. The panel of evaluators will be selected by a third party. In addition to meeting the qualifications criteria, each must have the ability to pass the initial Cellulite Severity Scoring (CSS) post-training test.

The following will not be disclosed to the evaluators:

1. Study device
2. Site names
3. Participant information

### 4.2.2 Frequency and Order of Evaluations

The evaluations will occur in advance of each planned interim analysis as outlined in **Table 3** and will follow the order outlined to ensure no pre-mature unblinding of the before/after that is required for the GAIS evaluation.

**Table 3 Independent Image Evaluation Scope**

Evaluation session number	Assessment type	Visit Time Points	Blinded
#1, at 3-month analysis	CSS ID of BL	Baseline and 30-day Baseline and 3-month	Yes, time point redacted
#1, at 3-month analysis, after CSS	GAIS	Baseline and 30-day Baseline and 3-month	No, improvement intentionally assessed
#2, at 6-month analysis	CSS ID of BL	Baseline and 6-month	Yes, time point redacted
#2, at 6-month analysis, after CSS	GAIS	Baseline and 6-month	No, improvement intentionally assessed
#3, at 12-month analysis	CSS ID of BL	Baseline and 12-month	Yes, time point redacted
#3, at 12-month analysis, after CSS	GAIS	Baseline and 12-month	No, improvement intentionally assessed

#### 4.2.3 Study Image Evaluation

At study photography visits, each participant will be photographed per the study photography manual to generate a minimum of three (3) images from a minimum of three (3) different angles (Section 4.1). The images for each participant will be available for the evaluator to assess per visit. The CONFIRM effectiveness outcomes are specific to the treated regions only, therefore, scoring will be considered on a participant level, but include scoring of the treated regions only. The treated regions will be disclosed to the evaluator by sextant (right buttock, right posterior thigh, right lateral thigh, left buttock, left posterior thigh, left lateral thigh) as well as a supplemental image set with an outline around the treated region per sextant. The training will also mimic this approach.

Evaluators will always be blinded to any participant ID, and for the CSS, the evaluator will not know which of the two (2) sets of images is before or after the index procedure. To further reduce bias, images will be scored under a different photo ID to ensure blinding is maintained. Evaluators will also be presented with two (2) sets of images where the set of three (3) angles of the same pre-treatment visit and three (3) angles of the post-treatment visit in a randomly assigned order (e.g., 3 pre-images on top of screen, 3 post images on bottom of screen or vice versa). Evaluators will be asked to identify which image is before and after the index procedure.

